## 5.3 Completion of Chemotherapy/Post-Treatment Evaluation

Three to eight weeks after completion of chemotherapy, patients will have the following assessments:

- CEA
- FACT-C questionnaire.
- Surgical assessment w/ endoscopy (sigmoidoscopy preferred, rigid proctoscopy acceptable) to evaluate the extent of residual tumor
- Rectal protocol MRI pelvis to evaluate ycT and ycN stage
- Digital rectal exam (DRE) to evaluate ycT stage

For patients with a cCR, non-operative management will be pursued. For patients with residual disease who do not meet criteria for cCR by 3-8 weeks after completion of the last cycle of FOLFOX or CAPOX, further therapy is recommended and at the discretion of the treating physicians. At investigator discretion, patients who achieve a near clinical complete response with equivocal findings concerning for residual disease may be followed closely with short interval observation (i.e. 6-8 week MR/endoscopic follow-up),

with non-operative management pursued if a subsequent cCR is achieved. Patients whose disease is amenable to transanal endoscopic microexcision (TEM) or local excision (LE) may undergo TEM/LE to evaluate degree of residual disease. For those with ypT1 disease without LVSI present, non-operative management may continue with evaluation noted above. For those with residual ypT2-3 disease or ypT1 with LVSI, extirpative surgery including TME is recommended with treatment at investigators discretion proceeding off-study.

Post-treatment lymph nodes are to be evaluated by imaging and reviewed in multidisciplinary tumor board with a radiologist and classified as progressive, persistent disease, indeterminate or benign. Patients with progressive or persistent lymph node disease will not be eligible for non-operative management and will undergo additional therapy. Patients with indeterminate or benign lymph nodes AND cCR of primary will undergo non-operative management.

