#### **5.4 Follow-up**

The FACT-C questionnaire and follow-up visit will be done 10-14 months from treatment (radiotherapy) start date.

Patients undergoing nonoperative management will be assessed for sustained cCR by rectal protocol MRI pelvis, endoscopy (sigmoidoscopy preferred, rigid proctoscopy accepted) and DRE every three months (not necessarily on the same day / appointment) for 1 year then every 3-4 months for the second year. If patient is unable to receive an MR pelvis every 3 months, every 6 months is acceptable as long as endoscopic exam is performed as per protocol schedule. CT chest and abdomen with contrast is to be obtained every 6 months for the first 2 years. Each of the follow-up studies and visits have a permitted variation of  $\pm 2$  weeks. After 2 years of follow-up on study, we recommend off-protocol follow-up with the same studies every 4-6 months per treating physician discretion.

Once a patient undergoes surgical resection they will undergo imaging and surgical follow-up as per institutional standard of care. These patients will continue to be followed for data collection for during study follow-up.

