## 13 STUDY CALENDAR

	Screening 	During RT	Day 1 of Each Cycle of Chemo 	Completion of Chemo 	10 to 14 Months after RT 	Follow-up 
Informed consent	X					
H&P	X	X (once)	X	X	X	
CBC diff, plts	X		X			
CMP	X		X			
CEA	X		X			
Pregnancy test 	X 					
Colonoscopy or barium enema or Hypaque enema	X 					
Surgical assessment with proctoscopy or sigmoidoscopy				X		X 
Digital rectal exam	X			X		X
Staging study to evaluate disease in abdomen and pelvis 	X					X
Staging study to evaluate disease in lungs 	X					X
Imaging study to assess local extent of primary tumor 	X		X 	X		X 
Radiotherapy		X 				
FOLFOX / CAPOX			X			
Biopsy for research (refer to Section 11)	X					
Blood for ctDNA 	X		X 	X	X 	X 
FACT-C	X			X	X	
AE assessment	AEs should be collected through 1 year following the start of RT					
Progression and survival						X

1. CT with contrast or MRI or PET/CT or PET/MRI; obtain every 6 months during the 2 years of follow-up. Once patients undergo surgical resection they will undergo imaging and surgical follow-up as per institutional standard of care.
2. CT of the chest or PET/CT; obtain every 6 months during the 2 years of follow-up. Once patients undergo surgical resection they will undergo imaging and surgical follow-up as per institutional standard of care.
3. Rectal protocol (pelvic) MRI (preferred), MRI, CT scan
4. Within 12 weeks of day of simulation for RT but no later than the first radiation treatment
5. Women of childbearing potential only
6. No more than 14 days prior to the first day of treatment
7. 5 fractions delivered over the course of no more than 10 business days (preferably starting on a Monday).
8. Chemotherapy should start 2 to 4 weeks after the end of RT. FOLFOX cycles are 14 days and a total of 8 cycles will be given; CAPOX cycles are 21 days and a total of 5 cycles will be given. Labs with each chemotherapy may occur up to 3 days prior to Day 1 of the cycle.

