## 14 DATA SUBMISSION SCHEDULE

Case report forms with appropriate source documentation will be completed according to the schedule listed in this section.

Form	Completion Schedule
On-Study Form Medical History Form	Time of registration
Radiation Therapy Form	Completion of RT
Chemotherapy Form	At the end of each cycle of chemotherapy
Disease Assessment Form	Baseline 8 weeks post-RT (OPTIONAL) 3-8 weeks post-chemoradiation
Follow-Up Form	Months 3, 6, 9, 12, 16, 20, and 24 (for subjects who have not undergone surgery only)
FACT-C	Baseline Completion of chemoradiation 10-14 months after chemoradiation
Research Tissue Form	Time of biopsy
Research Blood Form	Prior to the start of treatment Post-RT (with SOC CBC/CMP) Day 1 of Cycle 3 (FOLFOX) or Day 1 of Cycle 2 (CAPOX) Completion of chemotherapy (3-8 weeks after the end of chemotherapy) 10-14 months after RT Follow-up (Months 3, 6, 9, 12, 16, 20, 24) until salvage surgery or 2 years from the completion of chemotherapy, whichever is first
Adverse Events Form	Ongoing
Progression Form	Time of disease progression
Death Form	Time of death

Any queries generated by Washington University must be responded to within 28 days of receipt by the participating site. The Washington University research team will conduct a regular review of data status at all secondary sites, with appropriate corrective action to be requested as needed.

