### 18.4 Definition of Evaluability

Endpoint	In order to be evaluable for this endpoint, a patient must...
Primary	
cCR at completion of short course radiation therapy and chemotherapy	Have completed the evaluation after completion of radiation therapy and chemotherapy.
Secondary	
Progression-free survival at 2 years	
Incidence of any grade $\geq 3$ toxicity during treatment	Have received at least one fraction of radiation therapy and one dose of chemotherapy.
Incidence of post chemoradiotherapy grade $\geq 3$ toxicity	
Anorectal function per FACT-C at 1 year	Have completed a FACT-C at baseline and at least one post-treatment time point.
1 and 2 year organ preservation rate	Have received at least one fraction of radiation therapy and one dose of chemotherapy.
Exploratory	
Associate tumor microenvironment with cCR and other clinical outcomes	Have tissue collected at baseline, received at least one fraction of radiation therapy and one dose of chemotherapy, and completed evaluation of their disease.
Associate ctDNA levels with cCR and other clinical outcomes	Have blood collected at baseline and at least one post-dose time point, received at least one fraction of radiation therapy and one dose of chemotherapy, and completed evaluation of their disease.

All eligible enrolled patients that receive any treatment will be included in the intention to treat analysis. Patients that complete protocol therapy (both radiation therapy and chemotherapy) as prescribed will be included in a per protocol analysis.

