### 18.5 Data Analysis

Demographic and clinical characteristics of the sample will be summarized using descriptive statistics. Primary endpoint of the cCR rate will be reported as a proportion with 95% confidence interval (CI), and a one-sided asymptotic Wald test will be performed

to compare the study cohort cCR rate to the null value of 30%. PFS is defined as the time from date of treatment to death or progression, which occurs first. The alive patients without progression are censored as the last date follow-up. Kaplan-Meier method will be used to calculate PFS at 2-year. Proportions of any grade  $\geq 3$  toxicity during treatment, of post chemoradiotherapy grade  $\geq 3$  toxicity and organ preservation rates at 1 and 2 year will be calculated. Their corresponding 95% CIs will also be provided. The quality of anorectal function as measured by the FACT-C questionnaire is collected at screening, completion of chemo, and 1 year after RT. The generalized estimating equation (GEE) model with appropriate link function will be used to analyze this longitudinal data, in which the correlation among the repeated measures from the same patient need be considered. The autoregressive of first order as working correlation structure will be used and the patients with missing values at any time points will be excluded from GEE analysis. Least square means for quality of anorectal function at 1 year after RT will be estimated and 95% CI calculated within the use of GEE sandwich method when accounting for within-patient correlation.

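### The FACT-C GEE drops anyone missing one of three forms, against the 18.4 evaluability rule, and one Section 14 row dates the 1-year form from the wrong anchor

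*Combined protocol and SAP*

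**What the plan says.** Section 18.5 analyses FACT-C at three time points (screening, end of chemotherapy, 1 year after RT) by GEE with an AR(1) working correlation. The target is the 1-year mean: "Least square means for quality of anorectal function at 1 year after RT will be estimated". On missing data it says only that "the patients with missing values at any time points will be excluded from GEE analysis". It gives no imputation, sensitivity analysis or second FACT-C analysis.

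Section 18.4 defines who counts for the same endpoint: "Have completed a FACT-C at baseline and at least one post-treatment time point".

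The two post-treatment forms hang on different clocks. The middle one belongs to the visit in Section 5.3: "Three to eight weeks after completion of chemotherapy, patients will have the following assessments". The 1-year form is due "10-14 months from treatment (radiotherapy) start date" (Section 5.4). For resected patients, 5.4 adds: "These patients will continue to be followed for data collection".

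On the timing of the 1-year form, the Section 13 calendar column reads "10 to 14 Months after RT" and 18.5 also counts from RT. The FACT-C row in Section 14 reads "10-14 months after chemoradiation". In that same table the blood-sample row counts its 10-14 month draw from RT, as does the specimen table in Appendix F.

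**The concern.** The two rules define different populations for one endpoint, and the stricter one discards the quantity being estimated. GEE does not need complete triplets, so a missing middle form is no reason to drop an observed 1-year score. A complete-case estimate is in general unbiased only if forms are missing completely at random. Patients who leave the planned course before the post-chemotherapy visit could lack only the middle form and still return the 1-year form, and they may differ from the rest.

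At stake are the precision, the population and possibly the bias of the 1-year FACT-C estimate, which Section 2 uses to judge whether function is acceptable with the rectum preserved. The evaluable count reported in the Appendix F monitoring table would also differ from the number analysed.

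The timing row is a separate matter. Sites working from different sections would measure 1-year function at different times after treatment.

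**Working it through.** **Stated figure.** The documents give no FACT-C sample size or completion rate. The only sample size is N = 63, from the Simon design for cCR (18.2, 18.3). It reproduces: stopping at 8 or fewer of 24 and rejecting at 25 or more of 63 gives exact one-sided alpha 0.0497 and power 0.9033. I use N = 63 below.

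**Form patterns** (baseline, end of chemotherapy, 1 year; 1 = present)

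| Pattern | Evaluable (18.4) | In GEE (18.5) | 1-year score observed |
|---|---|---|---|
| 1,1,1 | yes | yes | yes |
| 1,0,1 | yes | **no** | yes |
| 1,1,0 | yes | **no** | no |
| 0,1,1 and 0,0,1 | no | no | yes |
| 1,0,0; 0,1,0; 0,0,0 | no | no | no |

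Patterns 1,0,1 and 1,1,0 are where the sections disagree. Only 1,0,1 loses a 1-year score from an evaluable patient.

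**Expected counts.** Assumption: each form is missing with probability m, independently of the others.

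| Quantity | Formula | m = 10% | 15% | 20% |
|---|---|---|---|---|
| Complete cases (18.5) | 63(1−m)³ | 45.9 | 38.7 | 32.3 |
| Evaluable (18.4) | 63(1−m)(1−m²) | 56.1 | 52.3 | 48.4 |
| Baseline and 1-year forms | 63(1−m)² | 51.0 | 45.5 | 40.3 |
| 1-year scores lost from evaluable patients | 63(1−m)²m | 5.1 | 6.8 | 8.1 |
| SE ratio, complete case to baseline + 1-year | √(1/(1−m)) | 1.054 | 1.085 | 1.118 |

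If every baseline form is present (it is a screening item), the loss is 63(1−m)m = 5.7, 8.0 and 10.1 scores, with the same SE ratio.

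**Using partial data as well.** Suppose a normal model with common variance and AR(1) correlation ρ is fitted to all 18.4-evaluable patients. Sum the information on the three visit means over the patterns 1,1,1, 1,0,1 and 1,1,0, weighting each by its probability. Invert, take the 1-year element, and compare it with the complete-case variance, which is proportional to 1/(1−m)³. For ρ = 0.4, 0.6, 0.8 the SE ratios are 1.062, 1.072, 1.086 at m = 10% and 1.133, 1.152, 1.182 at m = 20%. The complete-case rule therefore costs 6-9% and 13-18% in SE.

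**Timing.** Inputs: RT takes about 1 week and up to 10 business days, i.e. 2 weeks (6.1). The gap to chemotherapy is 2-4 weeks, CAPOX takes 15 weeks, FOLFOX 16 weeks, and total delay may reach 4 weeks (7.1). Counting full cycles from RT start, at 4.345 weeks per month:

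| Course | Weeks | Months | Section 14 window, months from RT start |
|---|---|---|---|
| Fastest | 1 + 2 + 15 = 18 | 4.1 | 14.1-18.1 |
| Slowest, no delay | 2 + 4 + 16 = 22 | 5.1 | 15.1-19.1 |
| Slowest, full delay | 2 + 4 + 16 + 4 = 26 | 6.0 | 16.0-20.0 |

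Section 5.4 gives 10-14 months from RT start. If the calendar's window is counted from RT end, the fastest course opens the Section 14 window at 10 months + 17 weeks = 13.9 months, an overlap of about 3 days. In Section 14 the term must mean the end of all treatment, because the Disease Assessment row uses it for the visit 3-8 weeks after chemotherapy.

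**The case against.** - **18.4 may be only a minimum condition, with 18.5 a deliberate subset for one model.** The wording allows this. But 18.5 holds the only FACT-C analysis of the endpoint, so the patients whom 18.4 admits with an incomplete set would appear in none. 18.4 is not a clean 1-year set either, since it admits patients with no 1-year score. That point stands.
- **The loss depends on the missingness pattern.** If a patient who misses the middle form always misses the 1-year form too, no 1-year score is lost for want of the middle form. Positive correlation between missing forms generally shrinks the 5-8 figure. This stands, and the counts are illustrations under independence.
- **Bias is not demonstrated.** Most patients resected after treatment would first attend the visit where the middle form is collected, so only earlier leavers fit the mechanism. This stands.
- **GEE on available data also generally needs data missing completely at random.** Correct. It recovers precision but does not reliably remove bias. A likelihood-based model is valid under the weaker missing-at-random assumption.
- **The Section 14 row looks clerical, in a table of form due dates.** Probably so. Counting to the last dose, the windows may overlap by a few days, and the ±2-week tolerance or early stopping of chemotherapy widens the overlap. The conflict remains.
- **The endpoint is secondary and unpowered (18.2).** Agreed. This limits the weight of the point but does not justify discarding collected data.

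**Conclusion.** The concern holds. The conflict between 18.4 and 18.5 is plain from the text. Under assumed independent missingness of 10-20% per form, the exclusion discards about 5-8 observed 1-year scores from evaluable patients. It raises the SE of the 1-year mean by about 5-12% on those scores alone, or by 6-18% against a model that uses partial data with AR(1) correlation 0.4-0.8. Bias is plausible, with presence and direction unknown. The Section 14 row is a separate, real inconsistency: after full planned chemotherapy its window falls at about 14.1-20.0 months from RT start, against 10-14 in 5.4. The primary cCR test is unaffected. The changes should be made before the FACT-C analysis.

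**What to change.** 1. In 18.5, delete the exclusion clause. Analyse every 18.4-evaluable patient with all FACT-C forms available, and name one main method: either the planned GEE on available data or a likelihood-based mixed model. The mixed model also relaxes the missing-data assumption.
2. Keep the complete-case GEE as a sensitivity analysis. Report forms received, and reasons for missing forms, at each time point.
3. Reconcile the Section 14 FACT-C row with the RT-anchored window in 5.4, the calendar and 18.5, so that all sites use one window. While doing so, settle whether it runs from RT start (5.4) or simply after RT (calendar, 18.5).

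The cost is one clause in 18.5 and one row in Section 14, with no added visits, forms or patients. Restricting to 18.4-evaluable patients still leaves unused any 1-year score from a patient without a baseline form. If baseline forms turn out to be missing, the sponsor may wish to include those scores too.

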## **18.6 FAK Expression and Tumor Microenvironment Analysis**

Rectal cancer biopsies will be assessed for total and phosphorylated FAK1 (Tyr-397, p-FAK1) and PYK2 (FAK2) by immunohistochemistry (IHC) as previously described. Rectal cancer samples will be stratified by high or low epithelial (tumor cell) p-FAK1 levels using IHC intensity and assessed for tumor-infiltrating CD3+, CD8+ cytotoxic T lymphocytes, neutrophil elastase and CD15+ granulocytes. Tumor fibrosis will be assessed by total collagen staining by Sirius Red and collagen I, III and IV deposition by IHC. Flow cytometry and IHC will be performed as previously reported. To investigate the relationship between tumor microenvironment (including FAK expression) or ctDNA levels with the outcomes of cCR, incidence of any grade  $\geq 3$  toxicity during treatment, incidence of post chemoradiotherapy grade  $\geq 3$  toxicity, and organ preservation rates, the logistic regression model will be considered. To investigate the relationship between tumor microenvironment (including FAK expression) or ctDNA levels with PFS, the Cox regression model will be considered. To investigate the relationship between tumor microenvironment (including FAK expression) or ctDNA levels with the outcomes of quality of anorectal function, the linear regression model will be considered.

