## 2 OBJECTIVES

Objectives	Endpoints	Justification for Endpoints
Primary		
To determine the clinical complete response (cCR) rate of patients with stage I-IIIB (cT1-3, N0-2a, M0) rectal cancer being treated with sequential short course radiotherapy followed by multi-drug chemotherapy.	cCR at completion of short course radiation therapy and chemotherapy	Nonoperative management treatment paradigms must be effective at eliciting a clinical complete response.
Secondary		
1. To determine the 2 year progression free survival (PFS) 2. To determine the incidence of any grade $\geq 3$ toxicity during treatment. 3. To determine the incidence of post chemoradiotherapy grade $\geq 3$ toxicity at 1 year 4. To determine quality of anorectal function at 1 year	1. PFS at 2 years 2. Incidence of any grade $\geq 3$ toxicity during treatment 3. Incidence of post chemoradiotherapy grade $\geq 3$ toxicity 4. Quality of anorectal function as measured by the FACT-C questionnaire at 1 year	1. Important to assess disease recurrence, metastasis and death when implementing new treatment paradigm. 2. Important to assess acute toxicity as there is concern that short course radiation is associated with significantly more acute toxicity.

using the FACT-C questionnaire.
 
5. To determine the 1 and 2 year organ preservation rate
	
5. Organ preservation rate at 1 and 2 years
	
3. Important to assess toxicity with new treatment paradigm, especially if rectum is not resected for nonoperative patients.
 
4. Treatment cannot be so toxic that even with preserved rectum patient QOL is poor.
 
5. Patients with cCR may still have regrowth of primary resulting in surgery. Need to assess how many patients can keep their rectum.

Tertiary/Exploratory		

1. To associate tumor microenvironment (including FAK expression) with cCR and other clinical outcomes.
 
2. To associate ctDNA levels with cCR and other clinical outcomes.
		

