## **18 STATISTICAL CONSIDERATIONS**

### **18.1 Study Objectives and Endpoints**

The primary objective is to determine the cCR response rate of patients with stage I-IIIB (cT1-3, N0-2a, M0) rectal cancer being treated with sequential short course radiotherapy followed by multi-drug chemotherapy (either 8 cycles of FOLFOX or 5 cycles of CAPOX). The endpoint is cCR at the completion of short course radiation therapy and chemotherapy. Secondary endpoints include PFS at 2 years, incidence of any grade  $\geq 3$  toxicity during treatment, incidence of post chemoradiotherapy grade  $\geq 3$  toxicity, quality of anorectal function as measured by the FACT-C questionnaire at 1 year, and 1 and 2 year organ preservation rate. Exploratory objectives are to associate tumor microenvironment (including FAK expression) and ctDNA levels with cCR and other clinical outcomes.

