## **18.7 Accrual**

The overall accrual will be 63 patients. The rate of accrual for the study is expected to be about 20 patients per year. It is expected that the accrual period of the study will be completed in about 3 years.

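### Section 18.6 splits p-FAK1 into high and low with no cut-point for the immune-infiltrate comparison and does not say how FAK enters the outcome models; a graded score would keep more information at almost no cost

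*Combined protocol and SAP*

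**What the plan says.** Section 18.6 has total and phosphorylated FAK1 and PYK2 measured "by immunohistochemistry (IHC) as previously described" in a cited study. The next sentence sets the grouping: "Rectal cancer samples will be stratified by high or low epithelial (tumor cell) p-FAK1 levels using IHC intensity". It goes on to assess those groups for T-cell and granulocyte infiltration. Fibrosis is read separately, by collagen staining and IHC.

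The section then lists the outcome models for the tumor microenvironment, including FAK expression, and for ctDNA:

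- For cCR, the two grade 3 or higher toxicity endpoints and organ preservation: "and organ preservation rates, the logistic regression model will be considered".
- For PFS: "ctDNA levels with PFS, the Cox regression model will be considered".
- For anorectal function: linear regression.

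None of these sentences gives the form of the FAK covariate.

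The analysis is exploratory. Section 2 lists it as "To associate tumor microenvironment (including FAK expression) with cCR and other clinical outcomes", and Section 18.1 repeats it: "Exploratory objectives are to associate tumor microenvironment (including FAK expression) and ctDNA levels with cCR and other clinical outcomes". Section 18.7 says "The overall accrual will be 63 patients". Section 18.4 limits the tissue set further; a patient must "Have tissue collected at baseline, received at least one fraction of radiation therapy and one dose of chemotherapy, and completed evaluation of their disease".

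I found no numeric cut-point, scoring scale, median rule or reader-blinding statement in Section 18.6. Nor is there one in the objectives (Section 2), tissue handling (11.1), endpoints (18.1), evaluability (18.4) or the monitoring tables (Appendix F).

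**The concern.** Two things are left loose.

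First, the one form of p-FAK1 that the plan defines is a two-group variable made from a reading that is graded to begin with. Every sample above the cut is treated as equal, and so is every sample below it. With at most 63 biopsies, that loss is material for the infiltrate comparison to which the sentence applies.

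Second, the covariate form in the outcome regressions is open. If the high/low variable were carried into them, the same loss would affect cCR, PFS and the other outcomes. With no cut fixed, the threshold could also be settled after outcomes are known, and a reported association could then not be told apart from one produced by the choice of cut.

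**Working it through.** **Inputs from the documents.** Maximum sample 63 (Sections 18.2, 18.7). cCR 30% under the null and 50% under the alternative (Section 18.2). There is no stated figure for the p-FAK1 analysis: no scale, effect size or power. The marker distributions and effect sizes below are therefore assumptions, shown with ranges.

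**The plan's only design figure.** The Simon design (stop if 8 or fewer of 24; reject if 25 or more of 63) is evaluated as the sum over x from 9 to 24 of P(X1 = x) × P(X2 ≥ 25 − x), with X1 binomial on 24 and X2 binomial on 39. This gives 0.0497 at a cCR rate of 30% and 0.903 at 50%. It reproduces, and p-FAK1 plays no part in it.

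**Step 1: information kept by a split.** For a normal marker cut at its q-th quantile c, the relative efficiency is φ(c)² / [q(1 − q)].

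| Cut | Information kept | 63 patients act like |
|---|---|---|
| Median | (1/2π)/0.25 = 2/π = 0.637 | 63 × 0.637 = 40 |
| 75th percentile | 0.539 | 34 |
| 90th percentile | 0.342 | 22 |

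**Step 2: the infiltrate comparison, which the split sentence does govern.** Simulation with n = 60, assumed correlation 0.35 between p-FAK1 and an immune readout, two-sided 5%:

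| Score | Spearman on the score | High/low comparison |
|---|---|---|
| Continuous, median split | about 75% | about 56% |
| Four levels, split at the middle | about 69% | about 57% |

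The loss is 75 − 56 = 19 points on a fine score and 69 − 57 = 12 points on a coarse one. A repeat run with 6,000 datasets per setting gave 74-75% against 56% for the continuous score, and 70-71% against 55-57% for three assumed four-level distributions.

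**Step 3: cCR, only if the split is carried into the logistic model.** Score test, cCR 50%, two-sided 5%:

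| Setting | Graded score | Split |
|---|---|---|
| n = 60, log-odds 0.8 per SD, continuous | about 81% | about 62% |
| n = 60, same effect, four-level | 75-76% | 61-64% |
| n = 63, OR 1.5 per SD, continuous | 35% | 23% |
| n = 63, OR 2.0 per SD, continuous | 72% | 52% |
| n = 63, OR 2.5 per SD, continuous | 90% | 72% |
| n = 40, log-odds 0.8 per SD, continuous | 62% | 42% |

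The n = 40 row matters because Section 11.1 makes repeat biopsy optional at affiliate sites that lack tissue.

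**Step 4: false positives, only if the cut is chosen on the outcome.** No true association, nominal two-sided 5%, cCR 50%:

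| Rule for the cut | Rejection rate |
|---|---|
| One cut fixed in advance at the median | about 4-5% |
| Best of three cuts (quartiles, or a four-level score) | about 12-13% |
| Best of 17 cuts, 10th to 90th percentile, n = 60 | about 30-32% |
| Any cut, 25th-75th / 20th-80th / 10th-90th percentile, N = 63 | 26% / 30% / 39% |

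**The case against.** The strongest reply is that the split sentence concerns laboratory readouts. Its second half compares immune infiltrates and involves no clinical outcome. The outcome models come later and speak of FAK expression without mentioning high or low. This stands: a reader might infer that p-FAK1 is reduced to two groups for cCR and PFS, but the documents do not say so. Steps 3 and 4 are conditional for that reason.

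A reader might also infer that an optimised cut is planned. Nothing proposes one; the text merely fails to exclude it. The figures near 30% and above also need a finely graded score, and no scale is stated. With four levels the upper figure is about 12-13%.

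A third tempting reading is that FAK is the leading marker or the main exploratory claim. Section 2 lists tissue and ctDNA as two exploratory objectives without ranking them, and Section 18.6 names many tissue readouts.

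The cited laboratory papers might contain a scoring rule. They cannot be checked here, and they are cited for how the assays are performed, not for the high/low threshold.

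Finally, the analysis is exploratory, with no alpha or decision attached, and Section 18.2 disclaims power even for secondary endpoints. That limits the importance of the point. It does not remove the loss in Step 2, which follows from the rule as written.

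**Conclusion.** The point holds as a cheap improvement. Section 18.6 prescribes a two-group p-FAK1 variable with no cut-point for the infiltrate comparison and leaves the covariate form in the outcome regressions open. Had the only complaint been the missing cut-point, it would be a matter of missing detail; what gives the point substance is that a better use of the same reading is available.

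For the infiltrate comparison, the cost is about 12 to 19 points of power at n = 60, assuming a correlation of 0.35. The lower figure applies to a four-level score and the higher to a continuous normal one. The cCR power loss and the false-positive inflation are conditional on choices the plan has not made, and their size depends on assumed effects and scales. At OR 1.5 per SD, for instance, both forms are underpowered and differ by 12 points. The direction of the loss is the same in every setting examined. The primary design and analysis are unaffected.

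**What to change.** In Section 18.6:

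1. State the p-FAK1 intensity score and its scale, and that it is read without knowledge of outcome.
2. Relate the score to the immune and fibrosis readouts by Spearman correlation.
3. Enter it as an ordinal or continuous covariate in the logistic, Cox and linear models.
4. Keep high/low for display only, with the cut fixed before outcomes are linked: for example the median, or the nearest score level if ties prevent an even split.

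The cost is SAP wording, with no new assays, patients or visits. It brings three small obligations: a check of linearity, a rule for ties on a coarse score, and a report of how many exploratory comparisons were made, since correlating p-FAK1 with many readouts adds multiplicity.

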### **5 EVALUATION STUDIES**

#### **5.1 Pre-treatment**

Within 12 weeks of day of simulation for RT but no later than the first radiation treatment:

- Examination by treating surgeon, medical oncologist, and radiation oncologist
- CBC with diff, CMP, CEA
- Staging study to evaluate extent of disease in the chest, abdomen and pelvis: CT w/ contrast is preferred to rule out metastatic disease

- Rectal protocol MRI pelvis to assess the local extent of the primary tumor, including T and N stage.
- Pregnancy test (for women of childbearing potential) – within 14 days of first treatment
- Colonoscopy (within 6 months is acceptable)
  - If feasible it is strongly recommended that the following physical findings should be scored:
    - Tumor location (distance in cm from the anal verge to the distal tumor margin)
    - Circumferential lesion Y/N
- Research biopsy (see Section 11.1)
- Blood for ctDNA (see Section 11.2)
- FACT-C quality of life questionnaire

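### The exploratory regression of FACT-C on tissue and ctDNA markers is left unspecified; naming baseline FACT-C as a covariate would usually sharpen it and would separate starting level from later function

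*Combined protocol and SAP*

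**What the plan says.** Section 18.1 makes the marker work exploratory: "Exploratory objectives are to associate tumor microenvironment (including FAK expression) and ctDNA levels with cCR and other clinical outcomes". For FACT-C, Section 18.6 says only "with the outcomes of quality of anorectal function, the linear regression model will be considered". It does not say which FACT-C score is the outcome, at which visit, whether as level or change, or with which covariates. The logistic and Cox models in the same section list no covariates either.

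The 1-year time point comes from the endpoint definition in Section 18.1, "quality of anorectal function as measured by the FACT-C questionnaire at 1 year".

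Baseline FACT-C is available. Section 5.1 lists the "FACT-C quality of life questionnaire" before treatment, and Section 18.5 says that the score "is collected at screening, completion of chemo, and 1 year after RT". Section 18.4 makes a patient evaluable for the FACT-C endpoint only on this condition: "Have completed a FACT-C at baseline and at least one post-treatment time point".

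The only other FACT-C model is in Section 18.5: "The generalized estimating equation (GEE) model with appropriate link function will be used to analyze this longitudinal data". It mentions no marker.

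**The concern.** Taken literally, 18.6 leads to a regression of a FACT-C score on a marker and nothing else. Two things could go wrong.

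The first is precision. A patient's score before treatment normally explains part of the score a year later. Leaving it out puts that variation into the residual, in a trial of at most 63 patients.

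The second is interpretation. Section 1.5 presents cell-free DNA as a measure of disease burden, and the FACT-C items in Appendix A include pain, weight loss, cramps, diarrhea and bowel control, which an untreated rectal tumor may affect. A marker that only tracks how unwell patients were at entry could then seem to predict function after treatment.

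The silence also leaves the choice of level, change or baseline-adjusted level open until results are seen, across a long list of markers.

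**Working it through.** **The plan's own figures.** Section 18.6 gives no figure for this regression. The only sample-size calculation is the two-stage design for cCR. It reproduces (exact type I error 0.0497 at 30%, power 0.903 at 50%) but has no bearing here beyond the total: "The overall accrual will be 63 patients".

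**Inputs.**
- N = 63 (Section 18.7), the most patients this regression could have.
- rho, the correlation between baseline and 1-year FACT-C. Not in the documents; assumed 0.3, 0.5, 0.7.
- c, the correlation between marker and baseline FACT-C. Not in the documents; assumed 0, 0.2, 0.3.
- Marker and scores are standardised, and the marker has no effect once baseline is known.

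**Standard error of the marker slope.**
- Marker only: sqrt(1 − c²rho²) / sqrt(N)
- Marker plus baseline: sqrt((1 − rho²) / (1 − c²)) / sqrt(N)
- Ratio, adjusted to unadjusted: sqrt((1 − rho²) / ((1 − c²)(1 − c²rho²)))

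| rho | c = 0: ratio | saving | c = 0.3: ratio | saving |
|---|---|---|---|---|
| 0.3 | sqrt(0.91) = 0.954 | 5% | sqrt(0.91 / (0.91 × 0.9919)) = 1.004 | about 0% |
| 0.5 | sqrt(0.75) = 0.866 | 13% | sqrt(0.75 / (0.91 × 0.9775)) = 0.918 | 8% |
| 0.7 | sqrt(0.51) = 0.714 | 29% | sqrt(0.51 / (0.91 × 0.9559)) = 0.766 | 23% |

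At c = 0 the adjusted model with 63 patients is as precise as an unadjusted one with 63 / (1 − rho²) = 69, 84 or 124 patients. The slope detectable with 80% power at two-sided 5% is (1.960 + 0.842) × sqrt(1 − rho²) / sqrt(63). It is 0.353 SD per SD unadjusted, and 0.337, 0.306 or 0.252 adjusted.

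**Shift in the unadjusted slope.** With no marker effect given baseline, the expected unadjusted slope is c × rho:

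| | rho 0.3 | rho 0.5 | rho 0.7 |
|---|---|---|---|
| c = 0 | 0 | 0 | 0 |
| c = 0.2 | 0.06 | 0.10 | 0.14 |
| c = 0.3 | 0.09 | 0.15 | 0.21 |

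**Check by simulation** (63 patients, 20,000 runs per setting).
- At c = 0 and rho 0.3, 0.5, 0.7, the slope SDs were 0.128, 0.129, 0.128 unadjusted and 0.124, 0.112, 0.092 adjusted.
- At c = 0.3 they were 0.129, 0.127, 0.127 unadjusted and 0.131, 0.118, 0.098 adjusted.
- Mean unadjusted slopes were 0.06, 0.10, 0.139 at c = 0.2 and 0.092, 0.148, 0.21 at c = 0.3. Mean adjusted slopes stayed within 0.002 of zero throughout.

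**The case against.** A reader might infer that the plan excludes baseline FACT-C. It does not. The text is silent, the model is only to be considered, and a baseline-adjusted or change-score analysis would be consistent with it.

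A reader might also infer that the marker associations are confounded. That needs a correlation between marker and baseline FACT-C, on which the documents give nothing; if it is zero, the shift is zero. The stated aim is association, and for a purely unadjusted association the crude slope is not biased. Adjustment asks a somewhat different question: association given starting quality of life.

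Nor can the full precision gain and the confounding be claimed together. The 5%, 13% and 29% savings need c = 0, while any shift needs c other than 0. At c = 0.3 and rho = 0.3 there is no gain.

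Finally, the exploratory rows of Section 18.4 do not require a baseline FACT-C, so an adjusted model could lose a patient who meets only those rows.

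All of this stands. It limits the size of the point and does not remove it: the plan does not name a covariate it already collects, and the adjusted slope is the one that separates later function from starting level.

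**Conclusion.** Section 18.6 leaves the FACT-C regression unspecified, and stating baseline adjustment would improve it at almost no cost. The gain in standard error lies between nothing and about 29% over the assumed ranges. The possible shift in an unadjusted slope runs from 0 to 0.21 SD per SD. Both rest on correlations that the documents do not supply, so neither loss of precision nor confounding can be stated as established. Severity is minor: the analysis is exploratory, Section 18.2 does not power the study even for secondary endpoints, and the secondary FACT-C estimate comes from the separate GEE.

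**What to change.** Add one sentence to Section 18.6, to this effect:

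*For each tissue or ctDNA marker, the 1-year FACT-C score (naming the total or subscale used) will be modelled by linear regression on the marker and the patient's baseline value of the same score, among patients evaluable for the FACT-C endpoint; the marker slope will be reported with its 95% CI.*

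The unadjusted slope may be shown alongside for readers who want the crude association.

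The cost is one degree of freedom, and any marker-evaluable patient without a baseline FACT-C drops out of the adjusted model. Baseline adjustment loses no one who is evaluable for the FACT-C endpoint, since Section 18.4 already requires a baseline form from them. No new data are needed.
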